8.2. Subject Self-Assessment Scale

For subjects enrolled to cohort 1, each subject will use the Subject Self-Assessment Scale to assess each Target DPN Lesions at the following visits: Visit 1, Visit 2 (prior to treatment), Visit 4 (prior to treatment), Visit 6, Visit 7 and Visit 8. For subjects randomized to cohort 2, each subject will use the Subject Self-Assessment Scale to assess each Target DPN Lesion at the following visits: Visit 1, Visit 2 (prior to treatment), Visit 3 (prior to retreatment, if applicable), Visit 4, Visit 5 (prior to retreatment, if applicable) Visit 6, Visit 7 and Visit 8.

Subject Self-Assessment Scale	
Grade	Descriptor
0	No Visible DPN Lesion
1	Mild; Slightly raised DPN lesion
2	Moderate; Obviously raised DPN lesion
3	Severe; Prominent DPN lesion

8.3. Subject Instructions

An investigational center staff member will dispense a Subject Instruction Sheet to each subject at Visit 1 (Refer to Appendix 15.1).

Throughout the study, the subjects should:

- Continue their routine cleansing regimen except they should avoid vigorous scrubbing of the Target DPN Lesions (*e.g.*, loofah, back brushes, scrubbing straps, abrasive washcloths, sponges and cleansing pads, etc.)
- Continue their routine cosmetics and skin care products
- Avoid exposing the Target DPN Lesions to excessive natural or artificial ultraviolet radiation (*e.g.*, sunlight, tanning beds) and use sunscreen on the Target DPN Lesions, if excessive exposure cannot be avoided
- Bring the subject instruction sheet with them to each visit.

On study visit days, the subjects should:

- When appropriate for the Target DPN Lesion location wear loose fitting clothing to the visit (Note: clothing that comes in contact with the study medication may be bleached)
- Starting with Visit 2, not apply any topical products to the Target DPN Lesions within 12 hours prior to the visit (Note: routine cleansing products are allowed)
- After the completion of any study visit where a study medication treatment was performed DO NOT:
 - Wash/submerge the DPN Target Lesions for at least 6 hours
 - Apply any topical products to the Target Lesions for at least 6 hours.
- Apply Aquaphor to the Target DPN Lesions the morning after the treatment visits (Visit 2 and Visit 4, cohort 1, or Visit 2, Visit 3 and Visit 5, cohort 2)

8.4. Other Study Supplies

Aclaris Therapeutics, Inc. will provide:

- An appropriate ruler, or other instrument, for measuring the thickness of the Target Lesions and the Lesion Dimensions
- 70% isopropyl alcohol for cleansing the Target DPN Lesion during the study medication treatment process
- White Petrolatum USP for protecting sensitive areas during study medication treatments for Target Lesions on the face
- Individual subject supplies of Aquaphor for Wound Care.

- Templates for use when identifying Target Lesions
- Supplies and instructions for collecting, labeling, shipping and result reporting for the clinical laboratory tests and urine pregnancy tests from a third party
- Equipment, supplies and training for taking standardized photographs
- Small Q-tip applicators
- Eyewash kits.

9. ASSESSMENT OF SAFETY

In addition to reporting adverse events throughout the study the investigator, a designated and appropriately trained staff member or the subject, will perform study following safety assessments according to the schedules noted below.

9.1. Local Skin Reactions (LSR)

The LSR assessment is the investigator's assessment of the signs and the subject's assessment of the symptoms associated with irritation at each Target DPN Lesion site, which includes the Target DPN Lesion and the area immediately surrounding the Target DPN Lesion.

Local Skin Reactions:

- Signs (assessed by the investigator):
 - Erythema
 - Edema
 - Scaling/dryness
 - Vesicles/bullae
 - Crusting
 - Erosion
 - Ulceration
 - Post-inflammatory hyper-pigmentation
 - Post-inflammatory hypo-pigmentation (does not include the superficial transient skin blanching/whitening related to the action of the study medications)
 - Atrophy
 - Scarring.
- Symptoms (assessed by the subject):
 - Stinging/burning
 - Pruritus (itch).

At Visits 2-8, the investigator and the subject will evaluate the LSR signs and the LSR symptoms at each Target DPN Lesion site respectively.

The investigator will assess the LSR signs as follows:

- Visits 2 and 4 (cohort 1) and Visits 2, 3 and 5 (cohort 2):
 - For each Target DPN Lesion site report the severity for all signs prior to any study medication treatment

- For every treated Target DPN Lesion site, 20 (\pm 4) minutes after the Treatment Completion Time, report the severity for the following signs:
 - Erythema
 - Edema
 - Scaling/dryness
 - Vesicles/bullae
- Visits 3 and 5-8 (cohort 1) and Visits 4 and 6-8 (cohort 2):
 - For each Target DPN Lesion site, report the severity for all signs.

The subject will assess the LSR symptoms as follows:

- Visits 2 and 4 (cohort 1) and Visits 2, Visit 3 and Visit 5 (cohort 2):
 - For each Target DPN Lesion site report the average of the severity over the previous 24 hours for all symptoms prior to any study medication treatment
 - For every treated Target DPN Lesion site, 10 (\pm 4) minutes after the Treatment Completion Time, report the average of the severity of the LSR for all symptoms since completion of the study medication treatment.
- Visits 3 and 5-8 (cohort 1) and Visits 4 and 6-8 (cohort 2):
 - For each Target DPN Lesion site, report the average of the severity over the previous 24 hours for all symptoms.

Both the subject and the study staff member will initial and date the source document to indicate the subject performed the LSR for symptoms as instructed. The staff member must not influence the subject's assessment.

The investigator should report the one integer that best describes the severity of each LSR sign for each Target Lesion site using the scale below. Each subject should report the one integer that best describes the severity of each LSR symptom for each Target Lesion site using the scale below:

Table 6 Grading of Local Skin Reactions

Local Skin Reactions	
Grade	Descriptor
0	None
1	Mild
2	Moderate
3	Severe

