4. STUDY DESIGN

This is a phase 2 open label study with an initial single arm safety cohort evaluating A-101 40% Topical Solution in subjects with DPN lesions. A second cohort will randomize subjects to two different treatment arms to evaluate different treatment schedules using A-101 40% Topical Solution. Refer to Figure 1: A-101-DPN-201 Study Design. Subjects may have up to 4 Target DPN lesions treated. Lesions that are selected for treatment must be on the subject's face or neck. Subjects will be required to complete a total of 8 study visits.

Cohort 1 A-101 40% Solution 12 Subjects Treatment Days 1 and 22

--

[figure not shown]

Figure 1: A-101-DPN-201 Study Design

The protocol defined study visits for cohort 1 are:

- Visit 1 (Day -13 to 0) screening
- Visit 2 (Day 1) enrollment and study medication treatment
- Visit 3 (Day 8) follow up visit
- Visit 4 (Day 22) follow up visit and second application of study medication if DPN target lesions meet criteria for retreatment
- Visit 5 (Day 29) follow up visit
- Visit 6 (Day 50) follow up visit
- Visit 7 (Day 78) follow up visit;
- Visit 8 (Day 106) follow up visit; end of study

The protocol defined study visits for cohort 2 are:

- Visit 1 (Day -13 to 0) screening
- Visit 2 (Day 1) randomization and study medication treatment
- Visit 3 (Day 15) follow up visit and second application of study medication if DPN target lesions meet criteria for retreatment
- Visit 4 (Day 22) follow up visit
- Visit 5 (Day 29) follow up visit and third application of study medication if DPN target lesions meet criteria for retreatment
- Visit 6 (Day 50) follow up visit

- Visit 7 (Day 78) follow up visit;
- Visit 8 (Day 106) follow up visit; end of study

Refer to Section 6 for a complete list of protocol required study assessments.

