7.5.2. Applying Study Medication to the Face

To apply the study medication to Target Lesions on the **FACE** the staff member will follow these treatment instructions:

- Do not apply the study medications to eyes, mouth, mucous membranes, open wounds
- Do not apply the study medication to the eyelids or within 5 mm of the orbital rim
- If, in the investigator's opinion it is needed to ensure no study medication enters the eye:
 - Position the subject in the supine position with the head slightly elevated and angled such that any excess study medication will flow away from the eye.
 - Aclaris Therapeutics will supply sites supplies of white petrolatum (100%) United States Pharmacopeia (USP) that is to be applied along the orbital rim and at the medial and lateral canthi; gently stretch the periorbital skin between the thumb and forefinger at the time of petrolatum application to distend any periorbital rhytides (e.g., "crow's feet") and ensure full coverage of the skin at the base of the rhytides to decrease the likelihood of tracking of the study medication towards the eye
 - Have the subject hold an absorbent pad in the appropriate area of the eye to absorb any excess study medication that might track away from the Target Lesion

- Instruct the subject to keep both eyes closed during the entire study medication treatment procedure
- After the subject is properly prepared and positioned, thoroughly cleanse the Target Lesion by firmly rubbing with a swab/wipe wetted with 70% isopropyl alcohol
- **Subjects randomized to ARM B of cohort 2 will have their DPN lesions medically abraded prior to the application of the A-101 study medication.
- Using firm pressure, while avoiding squeezing the applicator barrel, apply one drop of study medication onto the DPN lesion and then move applicator around in a circular motion to fully saturate the lesion. Using the smaller Q-tip applicator that is supplied massage the A-101 study medication into the DPN lesion for approximately 15 seconds.
- Minimize exposure to the surrounding normal skin
- During the treatment process remove excess study medication from the surrounding skin using a clean absorbent wipe
- Ensure the DPN Target Lesion is wet with study medication at the end of the ~15 second application
- Allow the DPN Target Lesion to remain undisturbed for ~60 seconds
- After ~60 seconds repeat the ~15 second application process

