10. ADVERSE EVENTS

10.1. Definitions

10.1.1. Adverse events (AE)

An adverse event (AE) is any untoward medical occurrence in a patient that develops or worsens in severity during the conduct of a clinical study of a pharmaceutical product and does not necessarily have a causal relationship to the study drug. An adverse event can, therefore, be any unfavorable and unintended physical sign, symptom, or laboratory parameter that develops or worsens in severity during the course of the study, or significant worsening of the disease under study (or any concurrent disease), whether or not considered related to the study drug.

- Accordingly, an adverse event could include any of the following:
- intercurrent illnesses
- physical injuries
- events possibly related to concomitant medication
- significant worsening (change in nature, severity, or frequency) of the disease under study or other pre-existing conditions. (NOTE: A condition, recorded as pre-existing, that is intermittently symptomatic [e.g., headache] and which occurs during the study should be recorded as an adverse event.)
- drug interactions
- events occurring during diagnostic procedures or any washout phase of the study
- laboratory or diagnostic test abnormalities occurring after the start of the study (i.e., after screening and once confirmed by repeat testing) that results in the withdrawal of the patient from the study, requires medical treatment or further diagnostic work-up, or is considered by the study investigator to be clinically significant. NOTE: Abnormal laboratory test results at the screening visit that preclude a patient from entering the study or receiving study treatment are not considered adverse events, but will be recorded to monitor data from patients who do not meet screening criteria.

Worsening of any of the Target Lesion assessments should be reported as an AE ONLY if the use of the study medication is interrupted or discontinued or if therapy is required to manage the event.

The investigator must, for any Target Lesion related AE, question the subject in detail to determine if there are any confounding factors (e.g., irritation by clothing or activity, sunburn) for any such AE.

The investigator should, when certain, report a diagnosis rather than the signs, symptoms or clinically relevant abnormal laboratory values associated with the AE. Otherwise, signs, symptoms or abnormal laboratory values may be used to describe the AE.

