10.2. Reporting Procedures

10.2.1. Procedures for reporting adverse events

At each post enrollment visit, the investigator or designee will question the subject to elicit AEs using a non-directive question such as “Has there been any change in your health since the previous study visit?”

The investigator or designee will monitor the subject for at least 20 minutes after the Treatment Completion Time at Visit 2 and at Visit 4 to elicit AEs in a similar manner.

If appropriate, based on the subject's response to non-directed questioning regarding AEs, the investigator or designee will follow-up with directed questions and appropriate evaluations.

Any AE noted during the reporting period must be reported in the source documents and on the appropriate AE CRF.

AEs that are defined as “Not Related” to the study medications will be followed until they are resolved or until the subject’s last study visit. AEs that are defined as “Related” to the study medications will be followed until they are resolved or, if not resolved after the subject’s last study visit, until in the opinion of the investigator, the AE reaches a clinically stable outcome with or without sequelae.

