3.7.2 Local Skin Reaction (LSR)

For each visit, all predefined signs and symptoms at pre-medication and post-medication will be summarized by maximum severity cross all lesions for a subject. Number and percentage of subjects with grades 1, 2, 3, 4 will be tabulated for each sign (investigator)/symptom (subject) and at each visit. In addition, the maximum severity for each sign and symptom will also summarized cross all visits. Similar summaries will be presented for lesions. That is, number and percentage of lesions with grades 1, 2, 3, 4 will be tabulated for each sign and symptom at each visit and over all visits.

For treatment visits (ie, Visits 2 and 4 [cohort 1] and Visits 2, 3 and 5 [cohort 2]), for each sign (investigator assessment: Erythema, Edema, Scaling/dryness, Vesicles/bullae) or symptom (subject assessment: Stinging/burning, Pruritus [itch]) will be summarized using shift table. Severity grade shift from pre-medication to post-medication will be analyzed. Number and percentage of lesions with shifts will be presented. Number of treated lesions will be used as the denominator for percentage calculation.

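### Same-day safety checks were not fully adapted to Cohort 2: the 20-minute AE monitoring names the wrong visits, and the 20-minute sign list leaves out erosion and ulceration although Arm B is abraded first

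*Protocol*

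**What the plan says.** **AE monitoring.** Protocol Section 10.2.1 has staff monitor the subject "for at least 20 minutes after the Treatment Completion Time at Visit 2 and at Visit 4 to elicit AEs". It makes no distinction between cohorts. Those are the Cohort 1 treatment visits. For Cohort 2, Section 4 makes Visit 4 (Day 22) a follow-up visit and puts retreatment at Visit 3 (Day 15) and Visit 5: "Visit 5 (Day 29) follow up visit and third application of study medication if DPN target lesions meet criteria for retreatment".

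**Skin-reaction grading.** Section 9.1 lists 11 investigator-assessed signs, erosion and ulceration among them. On treatment days the full list is graded beforehand: "For each Target DPN Lesion site report the severity for all signs prior to any study medication treatment". Afterwards the investigator must, 20 (±4) "minutes after the Treatment Completion Time, report the severity for the following signs", and four are named: erythema, edema, scaling/dryness and vesicles/bullae. The visit numbers in 9.1 were adapted to Cohort 2, but the short list is the same for both cohorts and both arms. SAP 2.4.3.1 repeats it.

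**Abrasion.** Section 7.5.2 states: "Subjects randomized to ARM B of cohort 2 will have their DPN lesions medically abraded prior to the application of the A-101 study medication". Section 7.5.3 says the same for the neck.

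**AE rule.** Section 10.1.1: "Worsening of any of the Target Lesion assessments should be reported as an AE ONLY if" study medication is interrupted or discontinued, or therapy is needed.

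**Reporting.** For treatment visits SAP 3.7.2 provides a shift table: "Severity grade shift from pre-medication to post-medication will be analyzed". It covers the same four signs and two symptoms. SAP 3.7.2 adds that "the maximum severity for each sign and symptom will also summarized cross all visits".

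**The concern.** Cohort 2 came in with Amendment 1. Most visit-specific text was revised for it, but Section 10.2.1 still carries only the Cohort 1 treatment visits. Read literally, it asks for post-treatment monitoring at a visit where Cohort 2 receives nothing and is silent on two visits where it is treated.

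The sign list raises a different question. Abrasion is the only randomised difference between Arms A and B, and safety is part of the main objective. A mechanical procedure acts at once, so the same-day check is a natural place to see its effect. Yet the two signs that most directly describe broken skin are not graded at that check. If the pre-treatment grade is sometimes taken after abrasion, the Arm B shift table also mixes two different baselines.

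**Working it through.** No sample-size or power figure is involved. The check compares sections and counts visits.

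**1. Monitoring visits**

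| | Treatment visits (Section 4) | Named in 10.2.1 | Covered |
|---|---|---|---|
| Cohort 1 | 2, 4 | 2, 4 | 2 of 2 |
| Cohort 2 | 2, 3, 5 | 2, 4 | 1 of 3 |

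Cohort 2 has 24 subjects with at most 3 sessions each: 24 × 3 = 72 sessions. Visit 2 accounts for 24. The sentence in 10.2.1 does not reach the other 72 − 24 = 48.

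**2. Same-day sign grading.** Before treatment all 11 signs are graded; at 20 minutes, 4; at visits without treatment, all 11. So 11 − 4 = 7 signs have no post-treatment grade on the day, including erosion and ulceration. With 1:2 allocation Arm B has 24 × 2/3 = 16 subjects, hence up to 16 × 3 = 48 abraded sessions without such a grade. (This 48 is a different set from the one in step 1.) Photographs do not help: Table 3, footnote 12, schedules them before application on treatment days.

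**3. Whether AE reporting covers it.** It does so in part. Section 10.1.1 restricts when lesion worsening counts as an AE. Against that, 10.2.1 requires AE questioning at every post-enrolment visit, and footnote 18 to Table 3 keeps collecting AEs related to local skin reactions through Visit 8. A mild erosion that needs no therapy and does not stop treatment can still go unrecorded.

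**4. Order of grading and abrasion.** Section 9.1 places the first grade before study medication treatment. Two readings are possible:
- Sections 7.5.2 and 7.5.3 list abrasion among the treatment instructions, after alcohol cleansing, and Section 8.4 describes that cleansing as part of the treatment process. On this reading the grade precedes abrasion.
- Table 3, footnote 15, describes abrasion as done before treatment with A-101. On this reading a grade taken after abrasion also complies.

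An illustration of why it matters: erythema is 0 before abrasion, 2 after abrasion and 2 at 20 minutes. The SAP table shows a shift of 0 to 2 under the first order and 2 to 2 (no shift) under the second.

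**5. What a 20-minute grade can and cannot reach.** Next all-sign grading in Cohort 2, from Table 3:
- Session 1: Day 1 to Day 15, nominally 14 days (14 to 18 with windows).
- Session 2: Day 15 to Day 22, nominally 7 days (22 − 19 = 3 to 24 − 15 = 9).
- Session 3: Day 29 to Day 50, nominally 21 days (43 − 33 = 10 to 57 − 29 = 28).

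A grade at 16 to 24 minutes sees only what is visible then. An erosion that appears later and heals within these gaps is missed with or without the added grade.

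**The case against.** The strongest reply is that little is lost. At Visits 3 and 5 subjects are already assessed at 10 and 20 minutes, and Table 3 marks AE collection at both, so 10.2.1 is a visit-number slip. A short list of immediate irritation signs is a legitimate choice, and the documents do not say that abrasion causes erosion. Scarring and pigment change, the harms stressed in the Introduction, are graded at each later visit to Day 106. SAP Section 4 also says that a separate DPN indication is no longer pursued. All of this stands as a limit on weight. It does not make 10.2.1 correct for Cohort 2, and it does not supply a same-day grade of broken skin in the arm where skin is abraded.

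Four stronger readings are tempting and should be set aside:
- *Cohort 2 is unwatched after retreatment.* The 10- and 20-minute checks and the AE questioning contradict this.
- *The safety tables would show Arm B as no worse than Arm A.* Four signs and two symptoms are graded the same day in both arms and enter the shift table. Only signs off the short list escape.
- *The 14- and 21-day gaps are the size of the problem being fixed.* They come from the visit schedule, which the fix leaves alone.
- *The added grades make Cohorts 1 and 2 comparable.* They would do the opposite if they entered the across-visit maxima, because Cohort 2 would have up to three more chances per lesion to register these signs. SAP 3.1 puts the cohorts in adjacent columns.

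**Conclusion.** The concern holds as a minor point in three parts. First, Section 10.2.1 is wrong as written for Cohort 2: it covers 1 of 3 treatment visits and leaves up to 48 of 72 sessions unnamed, with limited practical harm. Second, erosion or ulceration visible on the day of treatment is not graded in any Cohort 2 session, including up to 48 abraded Arm B sessions, and AE reporting is only a partial substitute. Third, the order of pre-treatment grading and abrasion is ambiguous. The documents do not establish that grading after abrasion is plainly permitted, only that the text does not settle it.

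The counts are maxima. They assume full enrolment of 24, exact 1:2 allocation, retreatment of every subject at both visits, and abrasion at each Arm B session. No erosion rate is assumed. If abrasion causes none, the added grades will all be 0, which is itself safety information.

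**What to change.** 1. In Section 10.2.1, name the monitoring visits as *Visits 2 and 4 (cohort 1) and Visits 2, 3 and 5 (cohort 2)*.
2. In Section 9.1 and SAP 2.4.3.1, add erosion and ulceration to the 20-minute list at Visits 2, 3 and 5 for both Cohort 2 arms, and add both signs to the SAP 3.7.2 shift table. Use them for the Arm A versus Arm B comparison only, and exclude these 20-minute grades from the across-visit maximum-severity summaries shown beside Cohort 1.
3. In Section 9.1 and SAP 2.4.3.1, state that pre-treatment skin reactions are graded before any abrasion and before any study medication.

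The cost is at most 2 signs × 4 lesions × 3 sessions = 24 extra grades on the 0–3 scale per Cohort 2 subject, at an assessment that already takes place. Visits, treatment and efficacy scoring do not change. If Cohort 2 has already been treated, the sponsor can still report the grading order that was used and footnote the skin-reaction tables to say which signs have no same-day post-treatment grade.

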- Repeat the application/waiting cycle until the study medication has been applied to the DPN Target Lesion up to 3 times.

Record the number of times each Target DPN Lesion is treated during a treatment visit and record the time the final treatment is completed for the last treated Target DPN Lesion as the Treatment Completion Time.

It is acceptable to treat multiple Target DPN Lesions at the same time if, in the investigator's opinion, it is practical without exposing non-lesional skin to the study medication.

After completing the study medication treatment to the Target DPN Lesion do not disturb the DPN Target Lesion until just prior to the subject's post-treatment LSR evaluation.

Just prior to the subject's post-treatment LSR evaluation absorb any remaining study medication and gently dab or otherwise dry the Target DPN Lesion with an absorbent pad or dry gauze without wiping or rubbing.

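### Cohort 2's acute skin-reaction ratings are timed to the drug and not to the abrasion, so stinging during abrasion and same-day erosion, ulceration or crusting can be missed; two added rating items and one clarified time point would close the gap.

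*Protocol*

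**What the plan says.** Protocol 7.2 and SAP 2.3.2 give both Cohort 2 arms the same drug on the same treatment days; abrasion is the only difference. Protocol 7.5.2 (face) and 7.5.3 (neck) place abrasion after alcohol cleansing and before the first drop: "Subjects randomized to ARM B of cohort 2 will have their DPN lesions medically abraded prior to the application of the A-101 study medication".

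The acute LSR ratings are in Protocol 9.1 and are repeated in SAP 2.4.3.1:

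- **Signs, before treatment.** "For each Target DPN Lesion site report the severity for all signs prior to any study medication treatment". Eleven signs are listed.
- **Signs, after treatment.** At 20 ± 4 "minutes after the Treatment Completion Time, report the severity for the following signs": erythema, edema, scaling/dryness and vesicles/bullae only.
- **Symptoms, before treatment.** Stinging/burning and itch, averaged over the preceding 24 hours.
- **Symptoms, after treatment.** At 10 ± 4 minutes, subjects "report the average of the severity of the LSR for all symptoms since completion of the study medication treatment".

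The clock for both post-treatment ratings is defined in Protocol 7.5.2, where staff "record the time the final treatment is completed for the last treated Target DPN Lesion as the Treatment Completion Time". No time is recorded for the abrasion.

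For treatment visits, SAP 3.7.2 plans lesion-level shift tables on those four signs and two symptoms: "Severity grade shift from pre-medication to post-medication will be analyzed". It also tabulates pre- and post-medication severity separately by visit, and the maximum over all visits.

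**The concern.** Cohort 2 was added partly to learn what abrasion does, and abrasion is all that separates its arms. Its LSR ratings nevertheless start and stop with the drug. A symptom felt only while the lesion is being abraded has no rating window of its own. A sign that abrasion might produce at once, such as erosion, is on the protocol's list but not on the short list used at 20 minutes.

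Safety is part of the primary objective. SAP section 4 shortens the efficacy reporting but keeps the safety content of a full report. If abrasion causes brief stinging or short-lived erosion, the tables could show little sign of it in Arm B, and a reader choosing between the two procedures would not know that these items had not been measured.

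**Working it through.** The plan states no figure on this point, so there is nothing to reproduce. The check sets the order of events against the rating windows.

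**1. Order of events at an Arm B treatment.** Cleanse, abrade, apply drug (about 15 s on and 60 s wait, up to three applications), Treatment Completion Time, symptom rating at 10 ± 4 min, sign rating at 20 ± 4 min. The pre-rating comes before the drug; its place relative to abrasion is not stated. Both possibilities are set out below.

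| Item | Pre-rating before abrasion | Pre-rating after abrasion |
|---|---|---|
| Stinging during abrasion | In no rating | Averaged into a 24-hour recall and labelled pre-medication |
| Erosion, ulceration, crusting from abrasion | No same-day score | Scored, but labelled pre-medication and absent from the shift table |
| Erythema, edema, scaling, vesicles from abrasion | In the 20-minute score and in the shift | In the pre-medication table, and removed from the shift |

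Neither order gives a usable rating of stinging during abrasion. The other two rows depend on the order.

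**2. How soon the existing ratings follow abrasion.** Assume no pause between lesions, no wait after the last application, and abrasion either directly before the drug or all done at the start.

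- One lesion, three applications: 3 × 15 + 2 × 60 = 165 s = 2.75 min.
- Four lesions in sequence: 4 × 2.75 = 11 min.
- Symptom rating: from 2.75 + 6 = 8.75 min to 11 + 14 = 25 min after abrasion. Its recall opens only at completion, 2.75 to 11 min after abrasion.
- Sign rating: from 2.75 + 16 = 18.75 min to 11 + 24 = 35 min after abrasion.

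With a single application to one lesion, the two ratings start at 0.25 + 6 = 6.25 min and 0.25 + 16 = 16.25 min. Anything on the short list that lasts into these windows is recorded, whatever its cause.

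**3. Time to the next all-sign rating** (visit days and windows from Protocol Table 3, identical in both arms).

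| Treatment | Next all-sign rating | Nominal gap | Range with windows |
|---|---|---|---|
| Day 1 | Visit 3, Day 15 (+4), before retreatment | 15 − 1 = 14 days | 14 to 19 − 1 = 18 |
| Day 15 (+4) | Visit 4, Day 22 (+2) | 22 − 15 = 7 days | 22 − 19 = 3 to 24 − 15 = 9 |
| Day 29 (+4) | Visit 6, Day 50 (±7) | 50 − 29 = 21 days | 43 − 33 = 10 to 57 − 29 = 28 |

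Erosion, ulceration or crusting that resolves within the gap is not graded. Symptoms at these visits cover the previous 24 hours only, so they do not reach back to the procedure.

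**4. Effect on the summary.** With 24 subjects at 1:2, the planned arms are 24/3 = 8 (A) and 16 (B). Each Arm B subject whose event is missed lowers the Arm B percentage by 1/16 = 6.25 points. If a fraction c of the excess caused by abrasion is captured, observed difference = c × true difference. The documents fix neither the rates nor c. As an illustration with assumed rates of 10% in Arm A and 60% in Arm B, the true difference is 50 points; the table would show 50 at c = 1, 25 at c = 0.5 and 0 at c = 0. For stinging that ends before the drug treatment is complete, c is 0 or close to it. For erythema or edema still present at 20 minutes it may be high.

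**The case against.** A reader might infer that Arm B's acute abrasion harm goes mostly unrecorded, and that the safety comparison is therefore biased toward no difference. The documents do not support that, for four reasons.

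- **The mechanisms need opposite orders.** Subtracting abrasion erythema out of the shift requires a pre-rating after abrasion. That same rating covers all signs, so it would score erosion. Missing erosion requires a pre-rating before abrasion, and then the four-sign shift includes the abrasion effect. The two losses cannot be added together.
- **The implied order is pre-rating first.** The retreatment rule in Protocol 7.5 and SAP 2.3.3 uses the pre-treatment LSR grade, so the grade must be known before a lesion is retreated. Abrasion is also a step inside the application procedure. The rule is written for Visit 4, carried to Cohort 2 by reference, and does not apply at Visit 2, so this is an implication and not a statement.
- **Much is captured.** The four signs are graded at the lesion and surrounding skin regardless of cause. Persisting stinging is rated at 10 minutes, and every sign is rated again through Visit 8.
- **The comparison is descriptive**, by treatment actually received (SAP 3.7), with no between-arm safety test named.

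Other tempting magnitudes also fail. Seven of the eleven signs are not scored at 20 minutes, but four of them (the two pigment changes, atrophy and scarring) are late sequelae for which a 20-minute score would add little. The visit gaps apply equally to both arms. Cohort 1's Day 8 rating is a difference between cohorts, not between arms. Stinging during the drug applications is unrated in both arms and in Cohort 1; only the abrasion interval is specific to Arm B.

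All of this stands, and it limits the point. It does not remove it, because adverse event reporting recovers the missing items only in part. Abrasion at Visits 3 and 5 falls inside the reporting period. But Protocol 10.1.3 makes Visit 2 events before the first drug medical history, and 10.1.1 restricts when worsening of a target-lesion assessment counts as an event. Section 10.2.1 names post-treatment monitoring at Visits 2 and 4, although Cohort 2 is treated at Visits 2, 3 and 5; these passages need reconciling. Treatment-visit photographs are taken before treatment.

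**Conclusion.** The point holds as a cheap improvement, not as a defect that undermines the safety assessment. Followed as written, the plan has no usable rating of stinging or burning during abrasion. If the pre-rating precedes abrasion, it also has no same-day score for erosion, ulceration or crusting. For these items the descriptive comparison of Arm A with Arm B can understate the effect of abrasion.

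The size cannot be given: it depends on how often abrasion causes these reactions and how quickly they resolve, and the documents state neither. What is known is that the next all-sign rating is nominally 14, 7 or 21 days away, and that one missed Arm B subject moves that arm by 6.25 points at the planned size. There is no understatement if abrasion causes none of these reactions, or if they last until the next rating.

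The conclusion does not extend to erythema, edema, scaling, vesicles or persisting stinging. For these the shift reflects abrasion on the order the documents imply; stating that order would settle it.

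**What to change.** For Cohort 2, in both arms:

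1. State in Protocol 9.1 that the pre-treatment LSR is taken before cleansing and abrasion, and define the shift in SAP 3.7.2 as pre-procedure to post-procedure.
2. At the existing 10-minute rating, keep the current symptom item and add one covering the whole procedure, including any abrasion.
3. Add erosion, ulceration and crusting to the existing 20-minute sign list and to the SAP 3.7.2 tables.

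The visit, assessors and time points stay the same. The cost is a slightly longer form and some SAP wording. The added items have no Cohort 1 counterpart, so they can be compared only between Arms A and B. Keeping the current symptom item preserves the comparison with Cohort 1 on that measure.
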